Thiamine vs. Placebo to Increase Oxygen Consumption After Cardiac Arrest: Study protocol and statistical analysis plan

NCT02974257

Finalized and submitted to Clinicaltrials.gov: August 4, 2022

Principal Investigator and corresponding author: [name] [contact]

Introduction

The study protocol for Thiamine vs. Placebo to Increase Oxygen Consumption After Cardiac Arrest is summarized in the original posting for the trial on clinicaltrials.gov, NCT02974257. Additional details on the protocol and the statistical analysis plan are included in this document, which is being submitted for posting prior to unblinding or initiation of any data analysis.

Methods

Trial Design:

This is a randomized, double-blind, placebo-controlled trial of high-dose intravenous thiamine to decrease lactate and increase global oxygen consumption (VO₂) in patients who achieve return of spontaneous circulation (ROSC) after an in-hospital cardiac arrest (IHCA).

Consent:

Eligible patients will be intubated and sedated at the time of eligibility. Therefore, the legally authorized representative (LAR) will be approached by the research team, and written informed consent will be obtained prior to beginning the study protocol. If patients improve to the point of being consentable, they will be approached for consent for continuing participation.

Intervention:

Thiamine 500mg in 100mL 0.9% saline IV every 12 hours for 48 hours, with initial dose given within 12 hours of ROSC. Control arm will receive 0.9% saline of the same volume and frequency.

Patient Population

Inclusion Criteria:

- Adult patient (age ≥ 18 years)
- Cardiac arrest occurring while admitted to the hospital, with sustained (>20 minutes) return of spontaneous circulation (ROSC)
- Mechanically ventilated at the time of enrollment
- Within 12 hours of cardiac arrest event

Exclusion Criteria:

• Clinical indication for thiamine administration (alcoholism, known or highly suspected deficiency) or treatment with thiamine beyond the amount found in a standard multivitamin within the last 10 days

- Comfort measures only or anticipated withdrawal of support within 24 hours
- Severe agitation
- Protected populations (pregnant women, prisoners)

Randomization and blinding

The randomization will be done in a 1:1 ratio between treatment and control arms in blocks of four. Random assignments will be generated by computer, and a randomization list will be provided to and kept in the research pharmacy. A sealed envelope with arm assignment will be placed in each patient's chart for the unexpected and rare occurrence of the need to un-blind the study. Randomization will be stratified by screening lactate value, with stratification groups of lactate > 5 or ≤ 5 .

The research pharmacy, following the randomization list as above, will release study drug for each enrolled patient. Intravenous thiamine is odorless and colorless, and will be mixed in a 100mL bag of normal saline (NS). Patients assigned to the placebo arm will receive an identical volume of NS. It is not possible to tell the difference between thiamine and placebo using this method, and all study personnel with the exception of the research pharmacist will be blinded to the intervention. Unblinding will take place in the unlikely event of a case of suspected anaphylaxis or other severe reaction to study drug

Study Registration and Monitoring

The trial was registered at clinicaltrials.gov (NCT02974257) on November 18, 2016, prior to study start. Adverse events were monitored by the PI. There were no pre-specified stopping rules for futility or efficacy. No statistical interim analyses were planned. This trial was approved by the Internal Review Board (IRB) at Beth Israel Deaconess Medical Center.

Protocol:

Intervention: Thiamine 500mg IV in 100ml 0.9% saline every 12 hours for 48 hours (5 doses)

Placebo: 100ml 0.9% saline IV every 12 hours for 48 hours (5 doses)

Blood collection: Blood will be drawn at enrollment/time 0 (prior to study drug administration), 6 hours, 12 hours, 24 hours and 48 hours. Blood for all study labs will be collected by the patient's clinical nurse, using an existing intravenous or arterial line if present. Nursing or phlebotomy will perform a peripheral stick to obtain research blood only if no line is available for use. Research assistants will take all blood for immediate processing per the requirements of each lab test. Lactate and creatinine will be processed in the BIDMC clinical lab, and other clinical labs that will be obtained from the patient record include platelet levels and total bilirubin (for SOFA score calculation). All other research assays (see

list of secondary outcomes) will be completed in the BIDMC Center for Resuscitation Science Lab.

VO₂ monitoring: All patients meeting criteria for metabolic data collection (FiO₂ 60% or less and positive end expiratory pressure (PEEP) 15cm H₂O or less) will be connected to the VO₂ monitor at enrollment or as soon as the ventilator criteria are met, if still within 48 hours of enrollment. The monitor is made by General Electric, monitor version B650 with gas exchange module, and attaches in-line to the ventilator tubing, between the endotracheal tube and the Y-connector. All connections and disconnections of the monitor will be done by a trained respiratory therapist, with study staff present at the bedside. The tubing is attached to sensors that collect data breath-by-breath and that data is continuously recorded while connected to a laptop with dedicated software for this purpose. At the end of the study protocol all data will be downloaded and stored in a secure CSV file.

Cerebral Performance Category (CPC) and Cerebral Performance Category-Extended (CPC-E) score assessments: CPC and CPC-E will be assessed just prior to hospital discharge, at 30 and 90 days. Research staff will approach patients for assessment of CPC-E prior to hospital discharge. The CPC-E includes several questions testing logical thinking, attention and memory. The outpatient portion, which will be assessed in addition to the inpatient portion after hospital discharge/at 30 and 90 days, also includes questions about functional status and return to work. The CPC score will also be assessed by research staff prior to discharge. Phone calls to the patient will be made at 30 and 90 days (if the patient is no longer in the hospital).

Outcome Measures

Primary Outcome: Lactate change

Note: At the time of trial start, the primary outcome was change in oxygen consumption (VO_2) over 48 hours and change in lactate was a secondary outcome. After the first year, however, the primary outcome was changed to lactate, and VO_2 was changed to secondary. This change was made due to too many patients not meeting the ventilator criteria to allow collection of VO_2 data for at least the initial several hours of the study protocol, and enrollments therefore lagging behind. This change in primary outcome was posted at that time on clinicaltrials.gov and was submitted and approved by our Internal Review Board (IRB).

Prespecified Secondary Outcomes:

- 1. Change in VO₂ over 48 hours
- 2. Absolute level of lactate over 48 hours
- 3. absolute level and the change in oxygen consumption over 48 hours

- 4. absolute level and the change in pyruvate dehydrogenase (PDH) activity, quantity and specific activity over 48 hours
- 5. absolute level and change in creatinine over 48 hours
- 6. mortality (hospital discharge, 30 and 90 days)
- 7. Cerebral Performance Category (CPC) score (hospital discharge, 30 and 90 days)
- 8. Cerebral Performance Category-Extended (CPC-E) (hospital discharge, 30 and 90 days)
- 9. absolute level and the change in Sequential Organ Failure Assessment (SOFA) Score SOFA over 48 hours
- 10. renal failure during first 7 days following arrest
- 11. absolute level and change in cellular oxygen consumption rate over 48 hours

Sample Size Calculations:

Lactate: The analysis method for lactate will be linear mixed-effects modeling (LMM). This type of modeling is used in longitudinal or repeated-measures studies to consider the correlation of within-subject measurements and can optimize the power. In this case, we also want to include the interaction between arm (thiamine or placebo) and time, as our hypothesis is that the change of lactate over time will vary by arm. In this case, each subject will have lactate measurements at multiple time points, which are correlated. Since LMM will be used for the analysis, we have also used LMM for power analysis for this endpoint. We evaluated approximately 61 post-arrest patients in our databases, with similar characteristics to patients who will be included in this study, for whom we had lactate measurements over 24 hours. We observed that the post-CA patients have a mean lactate of 3.8±2.2 mmol/L at 6 hours, 3.5±2.2 at 12-hours, and 2.9±2 at 24-hours. We took a conservative position to assume that the potential effect size (the mean difference of lactate between the two arms) will be 33%. That is, we assumed that the mean lactate level at the three different time points in the thiamine arm would be 2.55, 2.35, and 1.94. Using LMM, accounting for an interaction between arm and time, and assuming a within-subject correlation of 0.7 with no decay in correlation over time, we will need 58 subjects (29 in each arm) to obtain >80% power with type-I error of 0.05 for detecting a difference in the change in lactate over 24 hours between arms. We assumed an average baseline (time 0) lactate of 4, and a standard deviation of 2. Our inclusion criteria restricts the patients population to those with a lactate >/=3, which is why we made our standard deviation slightly smaller. We also conducted a sample size calculation using the ANCOVA method for one baseline and 3 follow up lactate measurements. For this method we used the 24 hour means of 2.9 (+/- 2) and 1.9(+/-1.5), assumed a within-subject correlation of 0.7 between time points, and obtained target number of 54 patients (27 in each arm) to achieve 90% power with a type-I error of 0.05. To be conservative we will plan to enroll 60 patients, to account for possible drop out.

 VO_2 : Prior to our pilot study, there was no data on the effect of thiamine on VO_2 in hospitalized patients. We have therefore relied on our pilot data for the sample size calculation. In critically ill patients with preserved cardiac index (>2.4L/min/m²), the average increase in VO_2 after thiamine administration was 35mL/min. Using the average change in VO_2 of 35mL/min and the average standard deviation of 45mL/min, we will need to enroll 28 patients in each arm to achieve a power of 0.8 with a Type I error of 0.05. We have chosen to enroll 30 in each arm to allow some room for drop out.

Statistical Analysis General Principles

The statistical analyses and reporting will adhere to the CONSORT guidelines. All tests will be two-sided, a p-value <0.05 will be considered significant, and all confidence intervals will have 95% coverage. All analyses will be conducted on a modified intention-to-treat basis only including participants receiving at least the first dose of the study medication. In a double-blind trial, this approach is unbiased while increasing precision. Analyses will not be adjusted for covariates unless there are significant arm differences in baseline characteristics.

Baseline Characteristics

A description of the baseline characteristics will be presented by treatment arm. Categorical variables will be summarized by frequencies and percentages. Percentages will be calculated according to the number of patients for whom data are available. Continuous variables will be summarized using mean+/-standard deviation or median (interquartile range) based on the distribution of the data.

Analysis of Primary Outcome

We will compare repeated measures of lactate levels at each time point (0h, 6h, 12h, 24h, 48h) between arms using a linear mixed-effects model with an independent variance—covariance matrix to account for the correlation of within-patient repeated measures. Covariates in the model include treatment arm, time (as a categorical variable with five levels, defined as baseline, 6 hours, 12 hours, 24 hours, and 48 hours), and the interaction between treatment arm and time. Linear contrasts will be used to estimate the mean difference between treatment arms for each time point. If a patient dies before 48 hours, levels will be imputed by carrying forward the last known value before the event with a 20% penalty. A sensitivity analysis will be performed in which patients who die before 48 hours are assigned the last known value before the event without a penalty.

Analysis of Secondary Outcomes

Lactate levels over 48 hours

To test for a difference in absolute lactate level values, we will compare means or medians, as appropriate, between arms using either a Student's t-test or a Wilcoxon rank-sum test, respectively, at 6, 12, 24 and 48 hours.

Change in oxygen consumption (VO₂) over 48 hours

Prior to unblinding or analysis, oxygen consumption data will be cleaned using an algorithm designed by our research team in R version 4.1.1 (R Foundation for Statistical Computing, Vienna, Austria). This automated algorithm excludes VO₂ data (and the corresponding value for carbon dioxide production, or VCO₂) if one or more of the following criteria is met: all values recorded in the 10 min following a change in FiO₂ of 10%, all values recorded while FiO₂ is >61% (61% used in order to capture all situations when the ventilator is set for an FiO₂ of 60% or less, as the monitor reports this number to two decimal places and a set number of 60% may be recorded as 60.54%), all values deviating 15% or more from the mean of the previous five values and the next five values (i.e, deviating 15% from the mean of the ten neighboring data points), and all VO₂ values out of physiologic range unless these are persistent for more than 30 minutes, as these measurements are considered artifacts. Values that will be considered out of physiologic range are VO₂<80 mL/kg/min or VO₂>800 mL/kg/min. We allow these values if they persist for at least 30 min and if they are not excluded per the algorithm for other reasons, as critically ill post-arrest patients can sometimes have values well outside of standard normal range, due to temperature, medication use such as sedatives and neuromuscular blockade and/or alterations in metabolic function. The respiratory quotient (RQ) is calculated as the ratio of VCO₂/VO₂ at each time point. After data is run through the algorithm and still prior to unblinding, there is a final visual review of a graphical print-out of all data points for each patient to provide a secondary confirmation that values were kept or dropped appropriately.

To investigate the association between treatment and gas metabolism data (VO₂, VCO₂ and RQ) in the first 48 hours after ROSC, we will compare the area under the curve (AUC) for each oxygen consumption variable between the treatment arms. The AUCs for the oxygen consumption variables are influenced by the number of minutes of data available, which varies between patients. To account for this, AUCs for each patient will be adjusted by dividing by the number of minutes of oxygen consumption data available for that patient. Additionally, the AUCs for the VO₂ and VCO₂ variables are influenced by the weight of the patient, and thus will also be adjusted by dividing by the bodyweight of the patient, in kilograms. The median AUCs will be compared between treatment groups using the univariate Wilcoxon rank-sum test. To

control for the known effect of temperature on oxygen consumption, we will use quantile regression to compare median AUCs between patients using the treatment assignment as the predictor and average temperature as a covariate. To examine the association between treatment and the VO₂:Lactate Ratio, we will use a linear quantile mixed model (LQMM) with the VO₂:Lactate Ratio as the outcome variable, treatment as the predictor variable and temperature as the covariate. To account for clustering of VO₂:Lactate Ratio and temperature measurements within patients, we will add a random intercept for each patient to the LQMM. We will not control for vasopressor use or sedation in the above analyses unless use of these agents is significantly imbalanced between arms.

Pyruvate dehydrogenase (PDH), creatinine, SOFA score, and cellular oxygen consumption rate levels over 48 hours

To test change over time, we will compare repeated measures of each outcome listed above at each time point (0h, 24h, 48h) between arms using a linear mixed-effects model with an independent variance—covariance matrix to account for the correlation of within-patient repeated measures. Covariates in the model include treatment arm, time, and the interaction between treatment arm and time. Linear contrasts will be used to estimate the mean difference between treatment arms for each time point. To test for a difference in absolute values between arms, we will compare means or medians, as appropriate, using either a Student's t-test or a Wilcoxon rank-sum test, respectively, at 24 and 48 hours.

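### Patients who miss the ventilator criteria at enrolment enter the VO₂ data only if and when they qualify later, so the VO₂ comparison can be distorted if treatment affects who is measured or when

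*Combined protocol and SAP*

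**What the plan says.** - **Entry to the VO₂ data** (*VO₂ monitoring*, under *Protocol*). Recording needs FiO₂ no higher than 60% and PEEP no higher than 15 cm H₂O. Patients are connected "at enrollment or as soon as the ventilator criteria are met, if still within 48 hours of enrollment".
- **Order of events** (*Blood collection*). The first sample is taken at "enrollment/time 0 (prior to study drug administration", so enrolment comes before the first dose.
- **How common late qualification was** (note under *Primary Outcome*). VO₂ gave up its primary status after the first year: "This change was made due to too many patients not meeting the ventilator criteria" that would allow collection of VO₂ "data for at least the initial several hours of the study protocol". No count is given.
- **Cleaning** (*Change in oxygen consumption (VO₂) over 48 hours*). Among other filters, values recorded while FiO₂ exceeds 61% are removed.
- **Analysis** (same section). "AUCs for each patient will be adjusted by dividing by the number of minutes of oxygen consumption data available for that patient". The result is also divided by body weight. Median AUCs are compared by a Wilcoxon rank-sum test, then by quantile regression with average temperature as the only planned covariate. Vasopressors and sedation are added only if they are imbalanced.
- **Analysis set** (*Statistical Analysis General Principles*). "All analyses will be conducted on a modified intention-to-treat basis only including participants receiving at least the first dose of the study medication". The next sentence reads: "In a double-blind trial, this approach is unbiased while increasing precision". No exception is made for VO₂.

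**The concern.** Patients who meet both criteria at enrolment are identified before treatment. The rest are not. They join the VO₂ data when their oxygenation and ventilator course allow it, or never join because settings stay high or they die. Minutes at high FiO₂ are then removed from those who did join. All of this can follow the first dose, so treatment could in principle affect it.

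Dividing by available minutes equalises duration. It does not equalise who is observed or which part of the 48 hours is observed: a patient connected late contributes only a late window, yet is compared directly with one recorded from the start. A between-arm difference in VO₂ could then partly reflect which patients became measurable, and when, and not metabolism. VCO₂ and RQ come from the same recordings and share the problem.

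The plan deals with this kind of issue for other outcomes. Lactate has a rule for deaths and a sensitivity analysis, renal failure states how deaths are classified, and CPC-E is limited to survivors. For VO₂ there is no named subset, missing-data rule, sensitivity analysis or by-arm account of contributors.

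**Working it through.** **1. The plan's own figure.** *Sample Size Calculations* gives a difference of 35 mL/min, SD 45 mL/min, power 0.80 and 28 per arm. *General Principles* makes tests two-sided at 0.05.

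- Normal approximation: 2 × (1.960 + 0.8416)² × (45/35)² = 2 × 7.849 × 1.653 = 25.95, so 26 per arm.
- Two-sample t-test: 26.94, so 27 per arm.
- t-test figure divided by the Wilcoxon efficiency of 0.955: 28.2, so 29 per arm.

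The stated 28 is within this range. The figure is sound, but it assumes that every counted patient supplies VO₂ data.

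**2. Is selection after dosing possible under the text?** Enrolment precedes the first dose. Connection may occur up to 48 hours after enrolment. Patients who do not qualify at enrolment therefore generally enter after dosing, and the FiO₂ filter acts on later minutes too. The answer is yes.

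**3. Does anything in the plan remove it?** Blinding stops knowledge of the arm from influencing connection, but not an effect of treatment on FiO₂, PEEP or survival. The first-dose rule decides who is in the analysis set, not which of them have VO₂ values. Temperature adjustment does not address entry or timing. The answer is no.

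**4. Illustration of size.** The documents give no contribution rates, so everything here except the SD of 45 is assumed. Let a standard normal state L decide qualification, let VO₂ have SD 45 and correlation ρ with L, and let treatment have no effect on VO₂. If a share p of an arm is recorded (those with the highest L), the mean shift among recorded patients is

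45 × ρ × φ(z_p)/p, where z_p is the normal quantile of p.

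φ(z_p)/p is 0.798 at p = 0.5, 0.644 at 0.6, 0.497 at 0.7 and 0.350 at 0.8. For 60% versus 70% and ρ = 0.5, the bias is 45 × 0.5 × (0.644 − 0.497) = 3.3 mL/min. Simulation with 30 enrolled per arm gave, for ρ from 0.3 to 0.7:

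| Contributing, by arm | Bias (mL/min, absolute) | Wilcoxon type I error |
|---|---|---|
| 70% vs 70% | about 0 | about 0.05 |
| 60% vs 70% | 2 to 5 | 0.05 to 0.06 |
| 60% vs 80% | 4 to 9 | 0.06 to 0.11 |
| 50% vs 80% | 6 to 14 | 0.07 to 0.16 |

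The direction depends on the sign of ρ. The model does not represent unequal timing of recording, and it works in mL/min, whereas the planned statistic is a median AUC per minute per kg. For scale, the standard error of a mean difference at 28 per arm is 45 × √(2/28) = 12.0 mL/min.

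**The case against.** **The statement about bias is about something else.** It follows directly on the first-dose rule and most naturally justifies leaving out undosed patients in a blinded trial. A dosed patient with no VO₂ value is still in that set, with a missing outcome. This stands. A reader might infer that the plan makes a false claim about its VO₂ analysis, and the text does not go that far. What remains is that the statement is attached to all analyses with no exception, and its reasoning does not reach missing VO₂ data.

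**Nothing shows that treatment drives selection.** This also stands. The note on the change of primary outcome reports that patients did not qualify early on and that enrolment lagged. That may largely reflect status before treatment. It gives no number who never qualified and no sign that thiamine changes ventilator settings or survival. If treatment affects neither, selection works alike in both arms and the test stays valid, as the first row of the table shows.

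**The plan already acted on the limitation.** It moved VO₂ to secondary status, disclosed the reason, and made the VO₂ analysis in thiamine-deficient patients conditional on having enough data. That lowers the stakes. It does not tell a reader how to judge the VO₂ result that will still be reported.

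**The sizes are assumed.** This is correct. The SD of 45 is quoted beside a change in VO₂, not as the spread between early and late qualifiers. A 10-point gap in contribution hardly moves the type I error, and even the 9 mL/min figure is below one standard error.

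**A restricted analysis is not fully protected.** This is also correct, because dropped minutes and death can still truncate its data. It is nevertheless better protected than the only comparison now planned, because membership is fixed before dosing.

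**Conclusion.** The point holds as a gap in a secondary analysis. For patients not qualifying at enrolment, inclusion in the VO₂ data and the window observed are generally settled after dosing, and the plan has no provision for this. Distortion requires that treatment changes who becomes measurable, or when. The documents neither show nor exclude that.

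The size cannot be determined from the documents. Under the assumed model it runs from about nil with equal contribution to 14 mL/min at 50% versus 80%, against a planned effect of 35 mL/min. These figures are illustrations on a different scale from the planned statistic. Similar contribution and timing by arm would make a material bias unlikely, but the plan does not commit to reporting either.

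A reader might infer that the VO₂ comparison is biased, that a known fraction of the planned effect is artefact, or that the trial's main result is in doubt. None of these is supported: treatment-dependent selection is not shown, no contribution rates are given, and the primary outcome is lactate, which does not depend on the ventilator criteria.

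**What to change.** 1. Keep the planned AUC analysis. Prespecify a sensitivity comparison of VO₂, by the same methods, restricted to patients who met both ventilator criteria at enrolment, before the first dose.
2. State in *General Principles* and in the VO₂ section that the VO₂ comparison uses the subset of the modified intention-to-treat set with recorded data, and that the statement about absence of bias does not extend to it.
3. Tabulate by arm: number contributing, hours from first dose to connection, minutes retained after cleaning, and reason for no data (never qualified, died, other). Interpret any VO₂ difference in the light of this table.

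A rule that an effect may be claimed only if the two analyses agree is not recommended. Agreement would be hard to define, and in a trial of about 60 patients chance alone could decide it.

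**Cost.** The change is SAP wording and one table, with no change to patient care. Ventilator status must be assessed at enrolment to apply the connection rule, though the documents do not say that it is recorded. The document says that it was posted before unblinding or analysis; anything added after unblinding should be labelled post hoc.

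The restricted analysis has fewer patients and a wider interval. The share qualifying at enrolment is not given. If it were 70% of 30 per arm (21), the interval would be about √(30/21) = 1.20 times as wide and t-test power for 35 mL/min would be 0.69. At 50% (15), these become √(30/15) = 1.41 times and 0.54, compared with 0.84 if all 30 contributed. Later dropped minutes or death can still truncate its data, which is why minutes retained belong in the table.

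### The primary lactate model adjusts for neither time-0 lactate nor the randomisation stratum; always adjusting would narrow change intervals by about 3% (6 and 12 h) and 7% (24 h) with no new data

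*Combined protocol and SAP*

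**What the plan says.** All references are to the combined protocol and SAP.

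- **Statistical Analysis General Principles:** "Analyses will not be adjusted for covariates unless there are significant arm differences in baseline characteristics". The section sets a two-sided 5% threshold. It does not say which baseline variables are tested or what model follows if one differs.
- **Outcome Measures:** "Primary Outcome: Lactate change".
- **Analysis of Primary Outcome:** "Covariates in the model include treatment arm, time (as a categorical variable with five levels"; the only other term is the arm-by-time interaction. Time 0 is one of the five levels, so baseline lactate is a modelled outcome and not a covariate. Further: "Linear contrasts will be used to estimate the mean difference between treatment arms for each time point".
- **Randomization and blinding:** "Randomization will be stratified by screening lactate value", split at 5. No analysis section includes this factor.
- **Sample Size Calculations, lactate:** the mixed-model calculation was made "assuming a within-subject correlation of 0.7 with no decay in correlation over time". Also: "We assumed an average baseline (time 0) lactate of 4, and a standard deviation of 2". A second calculation is reported: "We also conducted a sample size calculation using the ANCOVA method for one baseline and 3 follow up lactate measurements".
- **Analysis of Secondary Outcomes:** the same three-term model serves PDH, creatinine, SOFA and cellular oxygen consumption. For VO2, temperature is named in advance as a covariate.

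**The concern.** Baseline lactate is the covariate most likely to predict later lactate, it is measured in this trial, and a screening value already drives the stratification. The planned model uses it only in part. The arm-by-time test does draw on the time-0 value, but it lets the two arms have different true means at time 0, which randomisation rules out. With complete data, the arm contrasts at each follow-up time are plain differences of arm means and gain nothing from time 0.

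The trigger does not fill the gap. Because allocation is stratified on lactate, a significant time-0 difference should hardly ever occur, so adjustment for the most useful covariate would hardly ever be made. For the other, unnamed covariates, the final model depends on chance baseline tests. At stake is precision in a 60-patient trial, and an analysis model that is not fixed in advance.

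**Working it through.** **Inputs** (lactate paragraph of Sample Size Calculations): baseline mean 4, SD s0 = 2; control means 3.8, 3.5, 2.9 with SDs 2.2, 2.2, 2 at 6, 12, 24 h; thiamine means 2.55, 2.35, 1.94; correlation rho = 0.7 at all lags; two-sided 5%; 29 per arm calculated, 60 patients planned. The arm differences are 1.25, 1.15 and 0.96.

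**Step 1: reproduce the plan's figure.** Take the joint 3-df test of arm-by-time over 0, 6, 12 and 24 h, with noncentrality (n/2) D'S⁻¹D. D is the vector of differences and S the covariance matrix of the three changes, with entries V_jk − V_0j − V_0k + V_00. At n = 29 the noncentrality is 11.17 and power 81.0% (80.0% with an F reference on 168 df). At n = 28 it is 79.5% (78.5%). So the stated 58 patients reproduce without baseline adjustment.

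**Step 2: the same test with baseline adjustment.** S becomes the covariance conditional on time 0, with entries V_jk − V_0j·V_0k/V_00.

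| rho | Power at 29 per arm, planned | Adjusted |
|---|---|---|
| 0.5 | 57% | 74% |
| 0.7 | 81.0% | 87.1% (noncentrality 13.01) |
| 0.8 | 94% | 96% |

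At 30 per arm and rho 0.7, power goes from 82.5% to 88.3%. These are large-sample figures.

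**Step 3: interval width for change from baseline.** The variance of a change is s0² + s1² − 2·rho·s0·s1. After adjustment it is s1²(1 − rho²).

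- 6 and 12 h: 4 + 4.84 − 6.16 = 2.68, against 4.84 × 0.51 = 2.468. Width ratio √(2.468/2.68) = 0.960.
- 24 h, SD 2 in both arms: 4 + 4 − 5.6 = 2.40, against 4 × 0.51 = 2.04. Ratio 0.922.
- 24 h, arm SDs 2 and 1.5 with baseline SD 2: 2.225 against 1.624. Ratio 0.854.

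Estimating the slope in 60 patients inflates the adjusted variance on average by 1 + 1/(60 − 4) = 1.018, so the width by √1.018 = 1.009. The ratios become about 0.969, 0.930 and 0.862, that is about 3%, 7% and 14% narrower. Simulated fitted intervals at 30 per arm (8,000 runs) agree: 3.1%, 6.9% and 13.8%.

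With the slope estimated, the 6/12 h and 24 h (equal SD) gains are about 9% and 13% at rho 0.5, and under 1% and about 4% at rho 0.8.

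**Step 4: interval width for the arm difference at one time.** The large-sample ratio is √(1 − 0.7²) = 0.714. Multiplied by 1.009 it is 0.72, about 28% narrower.

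**Step 5: how often the trigger would fire for time-0 lactate.** In simulated trials of 60 with stratified blocks of four (mean 4, SD 2, normal or lognormal), a t-test on time-0 lactate is significant in 0.2–0.3% of trials if screening and time-0 values coincide. If they correlate only 0.7 (an assumption), it is significant in 2.0–2.1%.

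**The case against.** The strongest reply is that nothing stated in the plan fails. That stands. Randomisation keeps the unadjusted estimate unbiased, the mixed model already uses time 0 as a response, and Step 1 confirms the stated power. A reader might infer that the trial is biased or underpowered as planned; the documents do not support either.

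A reader might also infer that the ANCOVA sizing contradicts the planned analysis. It does not. The mixed model is named as the analysis method, and ANCOVA was an additional calculation that gave the smaller number (54 against 58).

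The size can be overstated too. The variance ratios alone suggest 4% and 8% to 15%, but the cost of the slope removes about one percentage point. The figure near 14% also joins the unequal 24 h SDs of the ANCOVA calculation to the baseline SD of 2 given with the mixed-model calculation. Those ANCOVA inputs do not clearly lie behind the plan's own 27 per arm. With three follow-ups the variance factor is (1 + 2 × 0.7)/3 − 0.49 = 0.31. For a difference of 1.0 and 90% power, SD 2 in both arms gives 2 × (1.96 + 1.28)² × 4 × 0.31 ≈ 26.1, whereas SDs 2 and 1.5 (mean variance 3.125) give about 20.4, or 21 per arm.

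Chance imbalance is a weak argument for the primary outcome. If screening and time-0 lactate coincide, the 95th percentile of the time-0 difference is about 0.66 mmol/L. That shifts the 24 h change contrast by 0.3 × 0.66 = 0.20, against a planned half-width of 0.80. The 24 h level contrast shifts more, by 0.7 × 0.66 = 0.46.

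Finally, no gain has been computed for the stratum term, and none can be computed for the other repeated-measures outcomes. These points limit size and scope. None shows a disadvantage of adjusting.

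**Conclusion.** The point holds as a free improvement in precision that the SAP should adopt. For the primary change outcome the gain is modest: about 3% narrower intervals at 6 and 12 h and 7% at 24 h. It is about 14% at 24 h only if the arm SDs are 2 and 1.5 with a baseline SD of 2. For the per-time-point contrasts that the primary analysis names, it is about 28%. Joint-test power rises by about six percentage points at rho 0.7, by more if the true correlation is lower and by little if it is higher.

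The figures assume complete data and a fitted model that captures within-patient correlation. The primary analysis describes its covariance structure ambiguously; read literally as uncorrelated residuals, the planned change intervals would be wider and the gain larger. Imputing after death by a penalised carry-forward would alter the SDs and correlations. The smaller gain at 6 and 12 h rests on time-specific SDs; a common-variance random-intercept model gives the 24 h equal-SD figure throughout. No 48 h inputs are given, so nothing can be said about the size of the gain at the end of the primary window.

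**What to change.** Before unblinding, amend the SAP as follows.

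- State that the primary lactate model always adjusts for time-0 lactate, either by constraining the two arm means to be equal at time 0 or by taking time-0 lactate out of the response and entering it as a covariate with its time interaction.
- Include the lactate stratum (>5 or ≤5). This matches the analysis to the randomisation; little added precision is expected once time-0 lactate is in the model.
- Report both the change contrasts and the per-time-point contrasts from that model.
- Remove the significance trigger from the general principles. The VO2 section has a separate imbalance trigger for vasopressors and sedation, which this deletion does not touch.
- The same baseline handling can be applied to PDH, creatinine, SOFA and cellular oxygen consumption, but the documents give no inputs to size that gain.

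The cost is SAP wording and no new data. The covariate form uses four degrees of freedom for time-0 lactate over four follow-up times plus one for the stratum, so about five at most. The constrained form drops the time-0 arm difference and adds one term for the stratum.
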